APPENDIX H TISSUE MICROARRAY (TMA)

1. Collection of Specimen(s)

If patient consents to optional procedure(s), at least 2 and as many as 5 formalin fixed paraffin embedded blocks from nephrectomy will be acquired from each patient participating in the study. These blocks will be used for TMA analysis and for virtual karyotyping. A detailed laboratory manual will be provided.

2. Handling of Specimens(s)

Specimens need to be kept at ambient temperatures, and reasonable efforts should be undertaken to avoid exposure to temperature extremes. If necessary, samples may be shipped on gel packs to avoid extreme temperatures.

3. Shipping of Specimen(s)

Samples will be batch shipped to the University of Texas M. D. Anderson Cancer Center. All samples will be transported according to applicable IATA regulations.

Samples will be shipped to:

[name]
University of Texas M. D. Anderson Cancer Center
[name]
[name]
[contact]
[contact]
[contact]

4. Site(s) Performing Correlative Study

The analysis will be performed at the University of Texas M. D. Anderson Cancer Center.

5. Tissue Microarray Methods

Archival paraffin-embedded tissue will be evaluated by the PI or a dedicated pathologist, to select for areas containing viable cells. These areas will be used to construct TMAs. Technical work will be performed by a dedicated technician under the supervision of the PI and the pathologist.

Arrays will be constructed from 3 sites within each tissue block. The impact of heterogeneity on TMA readout validity has been assessed in other tissue types, with TMAs demonstrating comparable readout quality to standard immunohistochemical slides by using triplicate samples. Using a Beecher TMA device, three 0.6mm cores will be punched into each donor block, and transferred to a custom generated paraffin recipient block. Five micron-thick sections will be placed on a standard glass slide and will be stained using standard immunohistochemical techniques. Five μ m TMA sections will be mounted on slides, deparaffinized and hydrated. Section is then blocked and steamed, and appropriate antibody titer is applied overnight, rinsed, and appropriate secondary antibody is applied, followed by more rinses. DAB+ is then applied followed by rinse and DAB+ enhancer. The slide is then

placed in Hematoxylin followed by rinsing and bluing. Section is dehydrated; coverslip is placed.

Arrays created as outlined in will be stained with antibodies against the following proteins and others that may be deemed clinically relevant: Total AKT, AKT^{S473}, AKT^{T308}, p70 S6K, S6, phospho S6, p27, NFkB, mTOR, phospho mTOR. RCC-specific antibody optimization has already been performed by our lab.

6. Sample Analysis

Once staining has been performed, sample quantitation will be performed using an Ariol Image analysis system. Areas of viable tumor will be gated, and necrotic and nonviable regions masked. Acquisition characteristics will be set by the PI and the core facility staff. Percentage involvement of core by stain of interest will be captured as a continuous variable. Averaging of triplicate samples will be performed for each case. In the situation where significant outliers exist, scanning quality will be assessed and samples discarded if variability is due to low sample quality.

7. Statistical Analysis

Statistical Analysis will be performed according to guidelines in [Section 13.4](#) of the protocol.

**APPENDIX I CYTOKINE AND ANGIOGENESIS FACTOR ANALYSIS:
 [name], COLLABORATOR**

1. Collection of Specimen(s)

Venous blood will be collected for Cytokine and Angiogenic factors as outlined below.

Collect blood into 1x 10ml EDTA vacutainer (BD# 366457), 1 x 10ml SST vacutainer (BD# 367985), and 2 x 8ml Sodium Citrate CPT vacutainers (BD# 362761) following institutional procedures. All samples should be clearly labeled with the NCI Protocol Number, Subject Number, Specimen, and Timepoint using an indelible marker. A detailed laboratory manual will be provided.

2. Handling of Specimens(s)

Serum and EDTA treated Plasma Samples:

Allow the SST vacutainer to clot for approximately 20 minutes at room temperature prior to centrifugation. Centrifuge the SST and EDTA vacutainers at 1200xg for 20 minutes at 4°C. Remove the serum and plasma layers, respectively, and transfer to cryovials. Freeze serum and plasma samples at or below -80°C until shipment.

Sodium Citrated Plasma and Peripheral Blood Mononuclear Cell Layer (PBMC)

Samples:

Within two hours of collection, centrifuge the Sodium Citrate CPT vacutainers at 1500xg for 20 minutes at 25°C using only a swing-out head rotor. (Spinning CPT vacutainers in a fixed angle rotor may cause tube breakage). Without disturbing the mononuclear cell layer (cloudy white layer) remove the upper plasma layer and transfer to cryovials. Freeze plasma samples at or below -80°C until shipment. Next, remove 1.5ml of the mononuclear layer and divide among two cryovials. Add an equal volume of freezing media to each cryovial. (Freezing media consists of 80% RPMI-1640 (Cambrex 12-167F) and 20% DMSO (Sigma D8418). Mix thoroughly. Freeze PBMC cryovials overnight at -80°C using a controlled rate freezing container ([name]™, Nalgene 5100-0001). After 24 hours at -80°C, PBMC samples will be transferred to a liquid nitrogen freezer for long-term storage until shipment. **Note: Sites that do not have access to liquid nitrogen storage will submit serum and plasma samples only.**

3. Shipping of Specimen(s)

Samples will be batch shipped on dry ice to the University of Texas M. D. Anderson Cancer Center. All samples will be transported according to applicable IATA regulations. A detailed laboratory manual, as well as sample collection kits/shipping supplies, will be provided.

Samples will be shipped to:

[name]
University of Texas M. D. Anderson Cancer Center
[name]

[name]
[contact]
[contact]
[contact]

4. Site Performing Correlative Study:

Samples will be analyzed at the University of Texas M. D. Anderson Cancer Center.

5. Brief description of methods.

Multiplex bead assays (MBAs) will be analyzed using a BioPlex 200 machine (Bio-Rad) in the Blood-Based Biomarkers Laboratory (part of the [name]'s laboratory) at M. D. Anderson Cancer Center. Commercially available, validate, pre-made mixtures of beads will be used. Currently the profile consists of: 1) Bio-Plex 27-plex cytokine panel (BioRad, Cat# M50-0KCAF0Y); 2) Bio-Plex 23-plex cytokine panel (BioRad, Cat# M50-005KMII); and 3) smaller bead sets for EGF, TGFalpha, MMP-9, and E-Selectin (Lincoplex, HCYTO-60K-02 and HCVD1-67AK-02). Note that the final profile may be modified as new assays are developed. We have worked extensively with each of these assays in the past. [At this time, MBAs for osteopontin (OPN), IGF family members, Placental growth factor (PIGF), and several members of the VEGF family are in development and these factors would need to be assayed by ELISA (R&D Systems), volume permitting, if the MBAs are not available at the time of analysis. Because of sample volume constraints, a maximum of 3-5 ELISA assays can be conducted in addition to the MBAs.] Samples will be assessed in duplicate on the same plate. Plasma samples will be processed as per manufacturer's instructions. The combined MBA analyses, therefore, require less than 200 microliters of plasma. ELISA assays will be conducted as per manufacturer's instructions using a MicroQuant plate reader in the laboratory. For each plate, the standard curves will be assessed to ensure that the expected assay range is achieved (typically 0.2 or 2 pg/ml to 3,200 or 32,000 pg/ml depending on the marker)

The following assays will be performed and others will be added as appropriate.

Multiplex bead arrays

Bio-Plex 27-Plex Panel (BioRad) Cat# M50-0KCAF0Y

Bio-Plex 23-Plex Panel (BioRad) Cat# M50-005KMII

3-plex for Luminex: Human CVD Biomarker Panel 1, Catalog # HCVD1-67AK (MMP-9, sICAM-1, and sE-Selectin)

ELISA

Human Osteopontin (OPN) Quantikine ELISA Kit (R&D Systems) Cat#DOST00

Human Soluble Carbonic Anhydrase IX ELISA Kit (R&D Systems) Cat#DCA900

Human sVEGF R2/KDR Quantikine ELISA Kit (R&D Systems) Cat# DVR200

Human Collagen IV EIA kit (Argutus Medical) Cat#BIO82

Pro-angiogenic factors

VEGF
bFGF
EGF
TNF α
IL-6
IL-8
IL-1b
MMP-9
HGF
MCP-1
PDGF-bb
PIGF

Anti-angiogenic factors

IL-12p40/70
IFN-A2
IFN-G
MIG
IP-10

Inflammatory

ICAM-1

Markers of hypoxia

Osteopontin
sCA9
SDF-1 α

Endothelial function/damage

E-selectin
sVEGFR-2
Collagen IV

Other cytokines/chemokines

RANTES
MIP-1 α
MIP-1 β
Eotaxin
CTACK
GRO-A
MCP-3
MIF
MIG
TRAIL

Other interleukins

IL-1ra
IL-2
sIL-2RA
IL-3
IL-4
IL-5
IL-7
IL-9
IL-10
IL-13
IL-16
IL-17
IL-18

Growth factors

GM-CSF
G-CSF
M-CSF
SCF
NGF-B

Statistical Analysis:

We have investigated potential blood-based biomarkers in a randomized phase II trial of sorafenib vs. sorafenib and interferon. Using multiplexed bead assays (MBAs) and ELISAs to broadly assess a profile of cytokines and angiogenic factor (CAFs), we have identified plasma markers that predicted improved progression-free survival (PFS) in patients in each arm. A CAF signature, derived by combining individual markers, was more predictive than individual markers alone. *In vitro* studies and patient data suggest that CAFs may be regulated by tumor hypoxia, Akt/mTOR signaling, and other pathways. Based on this and additional studies in other cancer types, we *hypothesize that broad profiling of CAFs in plasma of RCC patients can be used to identify groups of patients that receive different degrees of benefit from different therapeutic regimen*. We also hypothesize that CAF profiling can identify markers of therapeutic resistance and tumor pathway activation. Our primary goal in this project is to develop predictive biomarkers of benefit (prolongation in PFS and overall survival, OS) using plasma specimens from this randomized phase II trial.

For the multiplexed bead arrays, the data is assessed in the following manner. For each plate, the standard curves are assessed to ensure that the expected assay range was achieved. For each individual sample, the mean concentration is calculated for duplicate samples, and the coefficient of variance % (CV%) is calculated for all analytes. If the median CV% was greater than 25%, analysis of the sample is repeated. In the rare case that the repeat CV% was greater than 25%, one of the two analyses is selected based on lower CV% and consistency with prior values.

The multiplexed beads are assessed in a similar manner. For each plate, the standard curves are assessed to ensure that the expected assay range was achieved. For each individual sample, the mean concentration is calculated for duplicate samples, and the CV% is calculated. If the CV% for an individual sample is greater than 50%, the value is rejected.

Two important issues impacting the potential utility of the CAF profiling are baseline variability and stability during storage and freeze-thaw cycles. To investigate these issues, we assessed two baseline plasma specimens (taken ~1 week apart) from 163 patients and 65 patients in two lung cancer trials, and two additional baseline serum samples from 144 patients in a separate trial. We found a high degree of correlation between the two baseline values. As expected, serum levels of VEGF were higher than plasma. We also assessed the effect of 1-4 freeze-thaw cycles or of storage at 4 °C for 48 hours compared to first thaw levels. Levels of all but one CAF (IL-5) were relatively stable (<20% change under these conditions), suggesting that CAF profiles should be relatively stable over 1-2 thaw cycles.

We are interested in changes in CAF levels from baseline (BL) that are associated with either tumor progression or are predictive of PFS. It is expected that approximately 80% of the patients will complete cycle 2. To identify potential markers of therapeutic resistance, we will fit linear mixed-effects models for each marker that is measured. These models will incorporate random effects that allow each individual patient to have his or her own natural level as well as a fixed binary effect for “progressed” versus “not progressed.” The significance of the fixed effect of progression is measured by an F-test. We will also explore more elaborate models that allow for a treatment effect that may distinguish changes on treatment from BL. To correlate changes in individual CAFs with clinical benefit from MK2206 vs. Everolimus, we will use Cox proportional hazards models. Primary analyses will use the differences in marker levels as continuous predictors. We will also explore the use of derived binary markers (“changed” or “unchanged”), where the thresholds for change will be set using mixed-effects linear models that incorporate repeated measures on the same individual patient. For the evaluation of markers to predict clinical benefit, we will take individual predictive markers and will combine them with the goal of identifying groups of patients with greater PFS and/or benefit. We will apply two different methods of analysis. First, we will fit multivariate Cox proportional hazards models that incorporate all individual markers that exhibit some predictive ability, using the Akaike Information Criterion (AIC) to eliminate markers that do not contribute significantly to the multivariate model. Second, we will apply robust clustering methods to identify subgroups of samples that exhibit similar CAF expression profiles, and test whether the resulting subgroups have different outcomes.

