13.2 Sample Size/ Power Calculation

Assuming that the median progression-free survival (PFS) is 4.9 months and 8.2 months for the everolimus and MK2206 arm, respectively and patients will be randomized with 2:1 ratio into the MK2206 arm and the everolimus arm, then with a total of 75 events (i.e., disease progression or death), we will have an 80% power to detect such a 67% increase in median PFS using one-sided log-rank test and at a 0.10 significance level. The total number of patients to be enrolled will be 105, with 35 on the everolimus arm and 70 on the MK2206 arm. The above calculation also assumes an accrual rate of 4 patients per month, thus it will take 26.3 months to accrue all 105 patients. The maximum study duration will be around 29 months, which include patients' accrual period and a follow-up period. East5 software was used for the sample size/power calculation.

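### Appendix I builds the cytokine signature by an undefined screen plus AIC and specifies no validation, so performance reported on the building patients would be biased upward

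*Combined protocol and SAP*

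**What the plan says.** The Statistical Analysis part of Appendix I sets the aim: "Our primary goal in this project is to develop predictive biomarkers of benefit", meaning longer PFS and OS, using plasma from this trial. For the signature, "we will take individual predictive markers and will combine them with the goal of identifying groups of patients with greater PFS and/or benefit". Two methods follow.

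- **Method 1** fits multivariable Cox models that "incorporate all individual markers that exhibit some predictive ability, using the Akaike Information Criterion (AIC) to eliminate markers" contributing little. The level of evidence that counts as predictive ability at the screening step is not given.
- **Method 2** clusters samples by CAF profile and will "test whether the resulting subgroups have different outcomes".

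The marker list is long and open: "The following assays will be performed and others will be added as appropriate". Section 13.2 fixes the patients available: "The total number of patients to be enrolled will be 105, with 35 on the everolimus arm and 70 on the MK2206 arm". It plans the PFS analysis at 75 events. Blood sampling is optional (Section 5.2 and the Section 10 calendar), so the number with CAF data may be smaller.

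Appendix I describes no split sample, cross-validation, permutation or external cohort for the signature. Appendix G, on karyotyping, does refer to a 0.632 bootstrap. Section 13.4 calls the correlative studies exploratory and says they cannot be powered.

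**The concern.** Method 1 uses PFS twice to choose markers: once in the single-marker screen and again in AIC elimination. The coefficients are then fitted to the same outcomes. A hazard ratio, C-index or p-value calculated on those patients carries the optimism of all three steps. The search is wide for the information available: 75 / 51 is about 1.5 events per listed candidate.

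At stake is what is taken from the trial into later work. Section 2.5 presents this analysis as a sequel to a five-factor signature from the team's sorafenib trial, so a signature found here may well shape a later design. If its apparent separation is largely selection, the later study starts from a false effect size. In addition, a claim that a signature is predictive needs a treatment interaction. Section 13.4 plans interactions for clinical benefit by logistic regression, but Appendix I plans none for the combined score on PFS.

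**Working it through.** **1. The plan's own figure.** The documents give no sample size or error rate for the signature. The only figure to reproduce is the main PFS power in Section 13.2: "we will have an 80% power to detect such a 67% increase in median PFS using one-sided log-rank test and at a 0.10 significance level". With the Schoenfeld formula, HR = 4.9/8.2 = 0.598 and 2:1 allocation:

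z = √(75 × 2/3 × 1/3) × |ln 0.598| − 1.282 = 4.082 × 0.515 − 1.282 = 0.82, so power = 79.4%.

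That agrees with 80%, so 75 events is a sound basis for what follows.

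**2. Number of candidates.** The Appendix I headings list 12 + 5 + 1 + 3 + 3 + 10 + 13 + 5 = 52 entries. MIG appears twice, leaving 51. The named panels would give 27 + 23 + 3 + 4 = 57.

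**3. Leniency of AIC.** AIC keeps a one-parameter marker when twice the gain in log-likelihood exceeds 2. For chi-square on 1 df that is p<0.157.

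**4. Chance that at least one noise marker passes the screen**, for independent markers: 1 − (1 − a)^51.

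| Screen a | Expected noise markers (51 × a) | P(at least one) |
|---|---|---|
| 0.05 | 2.55 | 92.7% |
| 0.10 | 5.1 | 99.5% |
| 0.20 | 10.2 | over 99.9% |

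**5. Null simulation of the whole procedure.** There were 105 patients, 2:1, accrued at 4 per month, with exponential PFS (medians 4.9 and 8.2 months) and analysis at 75 events. The 51 markers were unrelated to PFS, with a common pairwise correlation. Each run did a single-marker Cox score screen, then backward AIC elimination (at most the 15 best screened markers entered). The signature was then tested at 0.05 on the same patients, by model likelihood ratio and by log-rank on a median split. It was also frozen and applied to fresh null patients, using the same cut-point. A run in which no marker passed counted as no finding. Correlation and cut-off are assumptions, because the documents give neither.

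| Screen | Correlation | Same patients, likelihood ratio | Same patients, median split | Fresh patients, median split |
|---|---|---|---|---|
| p<0.05 | 0 | 94% | 81% | 5.5% |
| p<0.05 | 0.3 | 81% | 56% | 3.8% |
| p<0.05 | 0.5 | 62% | 37% | 2.2% |
| p<0.05 | 0.7 | 41% | 22% | 2.7% |
| p<0.10 | 0 | 98% | 91% | 4.2% |
| p<0.10 | 0.3 | 90% | 71% | 4.4% |
| p<0.10 | 0.5 | 69% | 48% | 4.0% |
| p<0.10 | 0.7 | 43% | 27% | 3.8% |
| p<0.20 | 0 | 99.5% | 99% | 5.0% |
| p<0.20 | 0.5 | 84% | 62% | 6.0% |
| p<0.01 | 0 | 41% | 33% | 1.8% |
| p<0.01 | 0.3 | 35% | 28% | 1.4% |

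Runs per row were 200 to 600, so the largest Monte Carlo standard error is √(0.25/200) = 3.5 percentage points. Fresh-patient rates below 5% partly reflect runs that produced no signature.

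**6. Smaller samples.** At p<0.05, the likelihood-ratio rate is 93% with 80% of patients (correlation 0). At correlation 0.3 it is 86% with 50% of patients and 81% in the MK-2206 arm alone. Optional sampling therefore hardly changes the result.

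**7. Repeat.** A separate simulation of the same setting (screens p<0.05 to p<0.20) gave 93–99% and 81–99% with independent markers, 37–41% and 18–26% at correlation 0.7, and 2–9% in fresh patients.

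**The case against.** Four points can fairly be made for the plan.

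- **The work is exploratory.** Sections 1.2 and 13.4 say so, and no primary or secondary clinical endpoint, stopping rule or treatment decision rests on the signature. This stands and limits the consequence. It excuses low power, but it does not make a biased performance estimate correct.
- **Same-patient evaluation is nowhere stated.** This also stands. Appendix I says how the first model is built, but not how its performance will be measured. The concern is an inference from there being no other evaluation set and from the use of this trial's specimens alone. The supportable claim is that validation is not specified.
- **A second method is planned.** Clustering as written does not use outcome to form the groups, so this selection bias does not reach it. A reader should not infer that the whole CAF analysis is compromised.
- **AIC is an acceptable tool.** Replacing it with a lasso or elastic net would be a preference. The gap is the missing validation of the full selection procedure.

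A reader might also infer that a significant signature is almost guaranteed from noise. That is so only for nearly independent markers with a lenient screen. Cytokines are likely to be correlated. At correlation 0.7 the rate falls to 41–43% by likelihood ratio and 22–27% by median split, and a p<0.01 screen gives 28–41% across both tests. The documents fix neither input, so they do not support the stronger statement.

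**Conclusion.** The point holds in this form: the signature for PFS is built by an undefined screen of 51 listed markers followed by AIC, in at most 105 patients and 75 events, with no validation specified. If performance is reported on those patients, the chance of a nominally significant signature from noise, for screens of p<0.05 to p<0.20, is about 40% to over 95% by likelihood-ratio test and about 20% to 99% by median split. In new patients it is about 5%. Every setting tried was well above nominal.

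This rests on same-patient evaluation, which is inferred, and on assumed values for correlation and cut-off. Appendix I also plans change scores and derived binary markers. These were not modelled and would widen the search further. The change should be made because it corrects a biased method, but the trial's clinical conclusions do not depend on it.

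**What to change.** Amend the Statistical Analysis part of Appendix I as follows.

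1. State the numerical screening cut-off and fix the candidate list before marker data are linked to outcome.
2. Keep AIC if preferred, but repeat both the screen and the AIC elimination within every fold of a repeated cross-validation, or within every bootstrap sample. The Appendix G wording should not simply be copied, because it describes resampling on features that have already been selected.
3. Report the out-of-fold or optimism-corrected C-index and hazard ratio as the signature's performance. Any same-sample figure should be labelled as apparent.
4. Test the interaction between the out-of-fold score and treatment on PFS before calling the signature predictive. With at most 35 everolimus patients this test will be weak, so a null result should be reported as inconclusive.

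The cost is appendix wording, a little more analysis code and less favourable reported performance. No patients, samples or visits are added.

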APPENDIX J MSKCC RISK STRATIFICATION

| MSKCC Risk Stratification | |
|----------------------------------|--------------------------------------|
| Karnofsky Performance Status | < 80 |
| Corrected Calcium | > 10.0 mg/dL |
| Hemoglobin | < Lower Limit of Lab Reference Range |

| Risk Groups | |
|--------------------|---------------------|
| Favorable | 0 Risk Factors |
| Intermediate | 1 Risk Factor |
| Poor | 2 or 3 Risk Factors |

NCI Protocol #: 8727
Version Date: June 11, 2018

